#### Good Clinical Practices

This study was conducted under Good Clinical Practices, in accordance with the Declaration of Helsinki, in compliance with the International Conference on Harmonisation (ICH) guidelines.

The Fontan circulation is a historic manifestation of our collective understanding of venous physiology and the essential function of the right ventricle. The procedure was established to reroute venous blood directly to pulmonary circulation in patients born with single ventricle physiology. The circulation has transformed survival patterns for such individuals. They now have a bright outlook such that they are in the vast majority able to survive to adult life. Fontan circulatory properties and function over time have revealed that the cardiovascular adaptations to the circulation have remained largely outside of the organisms ability to provide a responsive, stable oxygen delivery under low pressure to the peripheral tissue, resulting in a wide array of end-organ dysfunction, notably liver, and premature death or transplantation. The pulmonary vascular bed has emerged as a notable perpetrator of such adverse responses, dictating unfavorable late outcomes. Unlike other known culprits that inhibit this remarkable circulation, the pulmonary vascular bed holds great promise in that it is often amenable to manipulation and optimization through a wide array of new drugs that have emerged for the treatment of pulmonary hypertension. The pulmonary vasculature may also ultimately hold the answer to relieving the hemodynamic stress that induces fibrosis in the liver.

In this investigation we hypothesize the following:

- Exercise induces significant rises in venous pressures
- The resting and exercise induced rise in venous pressure is proportional to the degree of liver stiffness as measured by standardized ultrasound based techniques
- Use of locally delivered inhaled treprostinil, a pulmonary vasodilator will attenuate the degree of rise in venous pressures and subsequently the acute rise in liver stiffness

- The better hemodynamics associated with pulmonary vasodilation will result in greater exercise endurance

## 2. INTRODUCTION

### 2.1. Background

[figure not shown]
Thirty-five of every 100,000 live births are complicated by the presence of single ventricle physiology. If left untreated mortality for this condition is in excess of 80%. Fontan palliation was introduced in 1971 and has dramatically improved survival for these patients. The Fontan concept simply is centered on the surgical ability to re-route superior and inferior caval blood away from the heart, directly to the pulmonary arteries, thereby reestablishing full arterial saturations, and reducing the volume load imposed by initial surgical palliation of the single ventricle. For example arterial shunts such as the Blalock-Taussig-Thomas shunt result in significant pulmonary overflow that necessitates volumetric adjustment of the single ventricle to conserve systemic flow in the presence of augmented pulmonary blood flow.

The Fontan circulation has undergone many modifications over time. Currently, the Total Cavo-Pulmonary Connection (TCPC), consistent most commonly of an extra-cardiac tube graft, is the preferred surgical technique applied. It is associated with a decreased incidence of dysrhythmia, and has much better fluid dynamics and significantly less power loss across the circuit. It also has superior properties in terms of thrombotic risk. Not only are greater numbers of patients are now reaching adult life with this circulation, greater number of adults are reaching their 40's and 50's with the circulation, albeit with high proportion with Fontan failure and liver disease.

During late follow-up, functional capacity in Fontan patients is frequently severely impaired. Most patients appear to function at 50% of their predicted peak VO2. This impairment is associated with late morbidity and mortality. Peak VO2 is strongly predictive of midterm mortality and can also predict surgical mortality outcomes in this group. (Fernandes et al. 2011). Reduced Peak Vo2 also predicts unscheduled cardiac admissions.

Hepatic dysfunction is common among Fontan patients, particularly in the form of fibrosis and cirrhosis. The prevalence of hepatic changes during adult life is documented at up to 90%. The exact hemodynamic mechanisms involved however remain elusive in the literature. In a study of 32 Fontan patients with a follow-up of 12 years, hepatomegaly was present in 53%, coagulopathy in 58%, abnormal transaminase in 30%, elevated GGT in 30% and elevated bilirubin in 32%. (Camposilvan S et al, Liver and Cardiac function in the long term after Fontan Operation. Ann Thora Surg 2008; 86; 177-182). [name] et. al demonstrated significant exercise-induced systemic venous hypertension and co-existent, exercise-induced intensified renal and cerebral deoxygenation (i.e reduced cardiac output) in stable adult Fontan patients compared to healthy controls. The observations were thought to present a plausible premise for the development and perpetuation of end organ dysfunction such as hepatic fibrosis in the Fontan population ([name] et al, manuscript under review AJC, 2015). [name] et al. demonstrated in a longitudinal, prospective study examining 14 children with HLHS undergoing Stage 3 Fontan palliation that an

immediate and marked increase in liver stiffness occurs from near normal levels pre-Stage 3 Fontan surgery ( $1.18 \pm 0.26$  m/s) to mean liver shear wave speeds of  $2.27 \pm 0.34$  m/s after just the first 24-72 hrs post Stage 3 surgery. This elevated liver stiffness (as measured by shear wave elastography) was found to persist upon hospital discharge, at approximately 1 week post-op ([name] et al, *Effect of Stage 3 Fontan Operation on Liver Stiffness in Children with Hypoplastic Left Heart Syndrome*, manuscript under preparation.)

**Figure 1:** [name] et al: Box plot (Tukey) showing changes in liver shear wave speed over time in children undergoing stage 3 Fontan palliation. There is a significant increase in mean shear wave speed between baseline (pre-operative) and the first (post-operative) follow-up time point ( $p<0.0001$ ). There is no significant change in liver shear wave speed between follow-up time points #1 and #2, with means (and medians) being nearly identical ( $p=0.92$ ).

It is thought that increased liver stiffness (occurring as a result of high venous pressures in Fontan patients) promotes hepatic scar formation via mechano transduction signaling mechanisms that induces Myo-fibroblast (MFB) activation. MFBs facilitate collagen deposition leading to liver fibrosis and cirrhosis. *In vitro* studies comparing hepatic stellate cells and portal fibroblasts in soft unloaded liver matrices with stiff and loaded liver matrices, showed greater activation of MFBs occurred in the stiffer matrices with enhanced expression of Type I and III collagens. Rat Liver studies demonstrated that increased liver stiffness preceded the development of fibrosis in a carbon tetrachloride model of rat liver fibrosis. In addition to mechanical stimulation (increased pressure/stiffness) it is also thought that hypoxia precipitates liver fibrosis. Hypoxia-inducible factor-1 $\alpha$  (HIF1 $\alpha$ ) is induced following ischemia-reperfusion injury. It was found in a bile duct ligation (BDL) model of liver fibrosis that conditional HIF1 $\alpha$  deletion in cells of the liver and immune system led to reduced fibrosis compared with wild type animals. (Moon J-O, Welch TP, Gonzalez FJ, Copple BL. Reduced liver fibrosis in hypoxia-inducible factor-1 $\alpha$ -deficient mice. *AJP: Gastrointestinal and Liver Physiology*. 2009;296:G582-G592)

## 2.2. Preliminary Studies

Prior research has confirmed the safety of a variety of pulmonary vasodilator therapies in a wide spectrum of Fontan patients. Khambadkone et al (2005) demonstrated that elevated PVRi (pulmonary vascular resistance index) above 2 WU was common in well-functioning Fontan patients during late follow up. These patients were greatly responsive to exogenous nitric oxide (NO) demonstrating a drop in PVRi of 1.6 WU/m^2 with locally delivered NO. Safety has been established for a number of other advanced pulmonary vasodilator therapies. Bosentan did not change liver function in patients, but was also not associated with improvement in at least 3 open label studies. Other drugs with proven safety include sildenafil and iloprost. There are also a number of randomized trials currently in existence looking at the efficacy of pulmonary vasodilator therapy in Fontan patients. For example, there is a European double-blinded, placebo controlled trial looking at the effects of bosentan administration on exercise capacity in Fontan patients for which data collection has just been completed. The Paediatric Heart Network has also recently approved a trial of Udenafil to a similar end. The strength of this particular investigation is that it uses a primary endpoint (exercise endurance) that is particularly sensitive to hemodynamic changes and has therefore been used in many prior drug trials. A further strength is that this study employs semi-invasive monitoring of systemic pressures (which is equal to pulmonary artery pressures in this circulation) following drug administration. This potentially will allow the investigators to identify patients who are likely to respond to therapy by the particular characteristics of the pre-drug pulmonary arterial pressure profile.

[name] et al. demonstrated in a manuscript under review that significant exercise-induced systemic venous hypertension and cerebral deoxygenation occur in adult Fontan patients (not in healthy controls) and that this may represent a plausible mechanism for the development and perpetuation of end organ dysfunction such as hepatic fibrosis in Fontans. [name] et al demonstrated in another manuscript under preparation using a prospective study of children with hypoplastic left heart syndrome pre and post Stage 3 Fontan surgery that changes in liver stiffness occur acutely (patients on average had normal liver stiffness pre-operatively and sustained dramatic rises in liver stiffness 24-72 hrs post-operatively that persisted 1 week post-op).

## 2.3. Rationale for the Study

In this pilot study we propose to explore the effects of a locally delivered inhaled pulmonary vasodilator (inhaled treprostinil) on exercise performance, pulmonary blood flow, venous pressure response and vascular function in stable Fontan patients. We will also assess the effects of resting and acute rises in exercise induced systemic venous pressure on liver stiffness and will also assess whether treprostinil will attenuate the acute stiffness increase that we expect to see.

Specifically we will target the following endpoints in order to achieve these objects: exercise endurance (primary endpoint), and secondary endpoints including: systemic venous pressure, liver stiffness, peak VO2, VE/VC02 slope, Anaerobic threshold, Oxygen uptake efficiency slope, anaerobic threshold, Qp (pulmonary blood flow), augmentation

index, pulse wave velocity, flow mediated dilatation and laser flow Doppler %flow increase. We plan to use a prospective, randomized, double-blinded, placebo-controlled, crossover design.

The rationale for selecting these primary and secondary endpoints and trial design, is to identify potential predictors of responders to inhalation delivered pulmonary vasodilator therapies. Baseline hemodynamic and exercise characteristics may permit identification of factors associated with positive response in the primary outcome measure.

The Principal Investigator, at his previous institution, developed a novel, simple and safe non-invasive screening tool for estimating pulmonary arterial responses to exercise by measuring peripheral venous pressures in the upper limb. In the absence of pathway obstruction, venous pressures accurately reflect central pulmonary arterial pressures in Fontan patients. This system will be used to assess hemodynamic responses to pulmonary vasodilator therapy and will better classify which subset of patients has a more vigorous response.

### **3. PURPOSE OF THE STUDY**

The objectives of the study are:

**Primary Objective:** To assess the effect of locally delivered, inhaled, pulmonary vasodilator therapy (treprostinil) on cardio-pulmonary exercise test endurance.

Primary Research Hypothesis: Inhaled treprostinil will increase exercise endurance relative to placebo in stable Fontan patients without pathway obstruction or associated intra-cardiac lesions such as AV regurgitation or outlet or inlet obstruction.

#### **Secondary Objectives:**

To assess the effect of treprostinil on the following cardio-pulmonary parameters:

- the rate of rise of systemic venous pressures,
- pulmonary blood flow
- dynamic vascular functional responses including pulse wave velocity, brachial flow mediated dilatation, and venous structure and function (venous structure and function only performed at visit 1, pre-baseline exercise).
- The degree of liver stiffness at rest and the acute rise in liver stiffness induced by exercise

#### Secondary Research Hypotheses:

- Inhaled treprostinil will increase peak VO2 relative to placebo
- Inhaled treprostinil will decrease ventilatory equivalent for CO2 at the lactate threshold (VE/VCO2 at LT) and at peak exercise relative to placebo.
- Inhaled treprostinil will result in a higher estimated lactate anaerobic threshold relative to placebo
- Inhaled treprostinil will result in a superior oxygen uptake efficiency slope
- Inhaled treprostinil will result in an increase in pulmonary blood flow. We hypothesize that this effect will be more pronounced in patients noted to have a

more elevated rate of rise in systemic venous pressures with exercise at baseline relative to placebo

- Inhaled treprostinil will improve exercise related changes in rate of rise of systemic venous pressures
- Inhaled treprostinil will result in improved vascular function tests, specifically pulse wave velocity, and brachial flow mediated dilatation.
- Higher resting venous pressures will be associated with a greater degree of liver stiffness, and greater rises in venous pressures will induce proportional rises in liver stiffness
- Inhaled treprostinil will attenuate the degree of exercise induced acute liver stiffness

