### Visit 2 (Visit 2 will occur 1-2 weeks (+/- 3 days) after Visit 1)

- Insertion of venous cannula will be placed early in the visit to be used for taking venous pressure during the exercise testing.
- Vital signs (heart rate, blood pressure, oxygen saturation, height and weight)
- Blood drawn for metabolic panel (CMP), GGT, CBC (Drawn once at visit 2 or visit 3)
- Review of Concomitant Medications
- Urine pregnancy testing
- Resting ECG
- First dose of treprostinil OR placebo, as determined by the randomization following Visit 1.
- Participant blood pressure will be monitored for  $\frac{1}{2}$  hour (immediately, 15 min, and 30 min.) following the initial dose of treprostinil or placebo on a particular study day.
  - If systolic BP drops below 90 mm Hg or drops  $\geq 30$  mm Hg from the baseline, the participant's blood pressure will be monitored until return to above these thresholds. If baseline systolic blood pressure is below 90 mm Hg, then

the low threshold for additional monitoring will be 85 mm Hg for these participants.

- Study staff monitoring the blood pressure will consult with the PI or MD subI should a drop in blood pressure meeting these thresholds occur. Patient will continue with the investigation at the discretion of the PI or MD subI.
- Shear Wave Elastography (for liver stiffness)
- Vascular function assessment (Pulse Wave Velocity [PWV] and brachial Flow Mediated Dilation [FMD], already in use in this institution (described below).
- If the participant tolerated the 1st dose of treprostinil or placebo, (i.e no clinically significant drop in blood pressure or unexpected AEs deemed by the PI or MD subI to be related to study drug that would preclude the patient from continued participation) they will receive a 2nd dose of their assigned treatment (at least 2 hours after the first dose).
- If the patient did not experience a significant drop in blood pressure (as defined previously) following the 1st dose, then no further blood pressure monitoring will be required prior to the exercise test.
- If the participant experienced a drop in blood pressure (as defined previously) following the 1st dose, then blood pressure will be monitored for ½ hour (immediately, 15 min, and 30 min.) following the 2nd dose of treprostinil or placebo.

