  - If systolic BP drops below 90 mm Hg or drops  $\geq$  30 mm Hg from the baseline for visit 2/visit 3, the participant's blood pressure will be monitored until return to above these thresholds.
  - Study staff monitoring the blood pressure will consult with the PI or MD subI should a drop in blood pressure meeting these thresholds occur. Patient will continue with the investigation at the discretion of the PI or MD subI.
- Venous pressure manometer set-up (including calibration) will then be conducted prior to commencing exercise testing during which the venous pressures will be measured continuously during the exercise test.
- Maximal exercise testing/Ramp protocol (including spirometry).
- Immediately following exercise, a shear wave liver elastography will be repeated
- Post recovery, vascular function assessment (FMD and PWV) will be repeated.
- Light meal followed by a break for complete exercise recovery
- If the participant tolerated the prior dose of treprostinil or placebo, (i.e no clinically significant AEs deemed by the PI or MD subI to be related to study drug that would preclude the patient from continued participation) they will receive a 3rd dose of their assigned treatment.

- If the patient did not experience a significant drop in blood pressure (as defined previously) following the prior dose, then no further blood pressure monitoring will be required prior to the exercise test.
- If the participant experienced a drop in blood pressure following the previous dose, then blood pressure will be monitored for  $\frac{1}{2}$  hour (immediately, 15 min, and 30 min.) following the 3rd dose of treprostinil or placebo.
  - If systolic BP drops below the thresholds described previously, the participant's blood pressure will be monitored until return to above these thresholds.
  - Study staff monitoring the blood pressure will consult with the PI or MD subI should a drop in blood pressure meeting these thresholds occur. Patient will continue with the investigation at the discretion of the PI or MD subI.
- Endurance exercise test at 80% peak exertion to occur 2 hours after the maximal exercise testing. This is expected to last about 4-7minutes.
  - Venous pressures will be measured during the exercise test as described herein (see Venous Cannulation).
- The participants will be observed for 60 minutes following medication administration.
- Adverse event monitoring

The visit is anticipated to take 5-6 hours.

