## **9.2. Statistical Analyses**

Demographic and clinical characteristics of the patient population will be summarized using means and standard deviations or medians and interquartile ranges for continuous variables and frequency and percent for categorical variables.

The exercise endurance time (in seconds) will be compared between the two treatments (i.e. Treprostinil and placebo) using an analysis of variance (ANOVA) model for crossover designs. The terms in the model will include sequence, subject within sequence, treatment. Data will be assessed to determine if the normality assumption is plausible. If the normality assumption is not met, transformations will be applied in an attempt to satisfy the assumption (i.e. log, square root, rank). P-values  $<0.05$  will be considered significant.

Secondary outcome variables are continuous and will be analyzed using the ANOVA model for crossover designs as described for the primary outcome variable. For secondary outcome variable in which a baseline measure is taken, the change from baseline value will be used as the outcome variable and will be compared between treatment groups. Normality will be assessed and appropriate transformations used, if needed to satisfy the assumptions of the model. P-values  $<0.05$  will be considered significant.

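### The venous pressure–liver stiffness hypothesis has no planned analysis that can test it, and no resting venous pressure is scheduled at the time of the resting liver scan

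*Combined protocol and SAP*

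**What the plan says.** The pressure–stiffness relation is put forward in three places. The hypotheses listed before section 2 say that resting venous pressure and its exercise rise are proportional to liver stiffness. Section 2.3 says: "We will also assess the effects of resting and acute rises in exercise induced systemic venous pressure on liver stiffness". The Secondary Research Hypotheses in section 3 say of the resting state: "Higher resting venous pressures will be associated with a greater degree of liver stiffness". For exercise, the same item predicts that "greater rises in venous pressures will induce proportional rises in liver stiffness".

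On analysis, section 9.2 says of the crossover ANOVA: "The terms in the model will include sequence, subject within sequence, treatment". It then applies that model to the rest: "Secondary outcome variables are continuous and will be analyzed using the ANOVA model for crossover designs as described for the primary outcome variable". The section 9.1 list includes shear wave elastography but not venous pressure. The liver figure in section 9.3 concerns a change in stiffness, not an association.

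On timing, the Visit 2 list (repeated at Visit 3) runs: Dose 1, half an hour of blood pressure checks, resting elastography, vascular tests, then Dose 2 no sooner than 2 hours after Dose 1. Next, "Venous pressure manometer set-up (including calibration) will then be conducted prior to commencing exercise testing". The maximal test and a repeat scan follow. Table 1 agrees: the first scan sits in the column immediately after Dose 1, and venous pressure is first marked after Dose 2. Of the cannula, the visit list says: "Insertion of venous cannula will be placed early in the visit". Visit 1 has neither a liver scan nor a venous pressure.

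**The concern.** A stated hypothesis should have a model that contains its two variables and data that pair them sensibly. Here the model lacks one of the variables and the resting pair is taken at different times.

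Followed as written, the plan returns no answer on whether pressure and stiffness move together. Any answer would need an analysis chosen after the data are seen, with a free choice of visit, pressure reading and definition of rise. The analysis gap can be closed on paper at any time before unblinding. The timing gap cannot: a pressure not recorded at the scan cannot be recovered later.

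**Working it through.** **1. Can the planned model test the hypothesis?** The terms are sequence, subject within sequence, and treatment. The only contrast of interest is drug against placebo within participants. Venous pressure is not a predictor. The subject terms also absorb all differences between participants, which is where the resting hypothesis lies. No correlation, regression or mixed model with pressure as predictor appears elsewhere. The isotime comparison under Endurance Exercise Testing includes central venous pressure, but it too compares drug with placebo, and no liver scan accompanies that test.

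**2. How far apart are the resting readings?** Inputs: Dose 2 at least 2 h after Dose 1; first pressure after Dose 2; scan placed by Table 1 or by the visit list.

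- Table 1 (scan immediately after Dose 1): gap at least about 2 h.
- Visit list (scan after the 0.5 h of checks): 2 − 0.5 = at least about 1.5 h, less any further delay before the scan, plus set-up time.

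One dose falls between the two readings in either case. The stiffness rise (first scan to post-exercise scan) therefore spans Dose 2, while the pressure rise (pre-exercise to exercise) lies wholly after it. The intervening dose is active only at the treprostinil visit.

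**3. The plan's own sample size.** Section 9.3 gives 26 patients for 37 s with an SD of 65 s. The normal formula gives n = ((1.96 + 0.84) × 65/37)² = 24.2, so 25; the t-based calculation gives 27. The stated 26 reproduces. No figure is given for the association.

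**4. What 26 participants can show for the association.** By Fisher's z with one pair each, the smallest r with 80% power at two-sided 0.05 is tanh((1.96 + 0.84)/√23) = 0.526. Power is Φ(atanh(r) × √23 − 1.96). For r = 0.3, 0.4, 0.5 and 0.6 this gives 32%, 53%, 75% and 91%. An observed r of 0.5 would have a 95% interval of about 0.14 to 0.74.

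**5. Illustration of the timing loss.** Neither the true r nor k, the correlation between the later pressure and the pressure at the scan, is in the documents. Both are assumed. The observed correlation is taken as r × k, with scan-time pressure treated as the relevant quantity.

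| True r (assumed) | Simultaneous | k = 0.9 | k = 0.8 | k = 0.7 |
|---|---|---|---|---|
| 0.40 | 53% | 44% | 36% | 28% |
| 0.55 | 84% | 74% | 62% | 49% |
| 0.70 | 99% | 94% | 86% | 73% |

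The direction is certain under these assumptions. The size depends heavily on the true r.

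**The case against.** The best defence is that this is an exploratory pilot. Endurance is primary, and the listed secondary objectives are all treatment effects. That bears on how much weight the point carries, but it does not supply an analysis for a hypothesis the protocol states.

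A second defence concerns the resting half. It can be read as a statement about habitual pressure across patients, and then a pre-exercise value from the same day is a fair resting reading. This stands in part: on that reading the attenuation figures overstate the loss. Timing matters more for the rise-with-rise half, where the two changes cover different intervals.

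Third, sample size can matter more than timing. At a true r of 0.4, power is only 53% even with simultaneous readings. That stands, and is a reason to label the analysis exploratory.

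A reader might infer more than the documents support:

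- That the gap is a known 2 hours. That figure is the minimum dose interval; no scan time is given.
- That resting pressure is taken seated on the ergometer. The documents place the reading before exercise but state no posture for it.
- That the extra dose disturbs every pair. At the placebo visit it is inactive, so those pairs are drug-free, though still not simultaneous.
- That both visits would be pooled as independent observations. Nothing in the plan proposes this; it simply does not say which visit's values to use.
- That the trial rests on pressure causing stiffness. The resting half claims only an association; the exercise half does use causal wording.

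**Conclusion.** The concern holds. The planned ANOVA cannot test the pressure–stiffness hypothesis, venous pressure is missing from section 9.1, and no resting scan has a pressure scheduled at the same time. These points rest on the text alone. The gap of roughly 1.5 to 2 hours or more is inferred from the order of procedures.

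With 26 complete pairs the detectable correlation at 80% power is about 0.53, rising to about 0.59 with 20 pairs. The power losses from mistiming are illustrative and depend on an assumed true r and k. The primary endurance analysis is unaffected. The change should be made because it is cheap and the missing reading cannot be recovered afterwards.

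**What to change.** **Procedures (Visit 2 and Visit 3 lists, Table 1).** Zero the manometer and record one resting venous pressure at the time of the first elastography, using the early cannula. Keep the pre-exercise reading. Time-stamp the post-exercise scan so that it can be matched to the recovery pressures. The pressure rise can then be computed over the same interval as the stiffness rise.

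**Section 9.1.** Add venous pressure, and define the readings that give the resting value and the rise.

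**Section 9.2.** Prespecify, as exploratory:

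- (a) the resting association from placebo-visit values, one pair per participant, as the deciding analysis for the resting hypothesis;
- (b) a mixed model of the stiffness rise on the pressure rise over both visits, with a random participant effect and fixed treatment and period.

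State that 80% power with 26 participants needs a correlation of about 0.53, and report estimates with confidence intervals.

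The cost is one extra reading and zeroing at each of two visits, and one paragraph of analysis plan. No additional visit or participant is needed. If procedures can no longer change, the additions to sections 9.1 and 9.2 should still be made, with the non-simultaneous readings reported as a limitation.
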